Athens Greece 15. 11. 2024

ClinicalTrials.gov ID: NCT05623228

Brief Title: The Effectiveness and Efficacy of the Combination of the Integrated Psychological Therapy and Metacognitive Training. (ATHSCHIZ) (ATH22-24)

Official Title: The Effectiveness and Efficacy of the Combination of the Integrated

Psychological Therapy and Metacognitive Training in Schizophrenia and Treatment Resistant Schizophrenia. This is a Non-randomized Trial. The Therapy Lasts 60 Sessions.

[name]

Clinical psychologist and cognitive behavioral psychotherapist

Private practice

[name]

[name]

[contact]

[contact]

Links: URL: <https://www.linkedin.com/>

Description linkedin [name]

URL: <http://orcid.org>

Description orcid: [name]

[name]

Psychiatrist and cognitive behavioral psychotherapist

Private practice

[name]

[name]

[contact]

[contact]

Links: URL: <https://www.linkedin.com/>

Description linkedin [name]

URL: <http://orcid.org>

Orcid:[name]

Abstract

The aim of this study was to evaluate the effectiveness of the combination of Integrated psychological Therapy and the metacognitive training for psychosis. All the subprograms of IPT in 50 sessions and 10 sessions of MCT were offered in two biweekly one-hour sessions. 35 patients with schizophrenia took part in this study. Cognition, symptoms, functional outcome and recovery were assessed with a test battery before the therapy, after the therapy and in a follow-up after 6 months. General linear model and regression analysis were used. Significant effects were found in neurocognition, symptoms, functional outcomes and recovery. Effect sizes were also calculated. Significant effects were also found for the subgroup with treatment resistant schizophrenia in neurocognition, social cognition, symptoms, functional outcome and recovery. Effect sizes were also calculated. This study supports evidence for the effectiveness of the combination of IPT and MCT in Greece.

1. Introduction

Schizophrenia presents a chronic mental health disorder with a high vulnerability and a huge emotional and social burden. Schizophrenia and especially treatment resistant

schizophrenia (TRS) needs evidence-based and recovery-oriented pharmacotherapy and cognitive behavioral psychotherapy and rehabilitation. Pharmacotherapy presents the main therapy for patients with schizophrenia (Huhn et al., 2019; Leucht et al., 2013; Taipale et al., 2018; Wagner et al., 2021). The Integrated Psychological Therapy (IPT) presents an efficacious evidence-based rehabilitation program for patients with schizophrenia (Roder et al., 2008, 2010, 2011, 2013). It is also translated in Greek (Roder, 2007). Our research group has implemented Integrated Psychological Therapy (IPT) the last years in Greece ([name] et al., 2016, 2019, 2020, 2021). There are also other research groups in Greece that implemented IPT (Poulou, 2024). In other words, IPT is well known and established in Greece.

Metacognitive Training (MCT) for Psychosis presents also an efficacious and evidence-based therapy for people with schizophrenia and other psychotic disorders (Moritz et al., 2022; Penney et al., 2022; Veckenstedt & Scheunemann, 2023). MCT is implemented nowadays also in other mental health disorders, such as bipolar disorder and depression. MCT for psychosis is implemented for the first time in Greece in this research project. This is also the first study, as far as it is known, in which IPT will be combined with MCT. IPT and MCT present two therapy programs which are used in our private practice systematically. The main hypothesis is: The combination of IPT and MCT is effective and efficacious. The therapy shows improvement in cognition (neurocognition, social cognition), in psychopathology, in functional outcome and recovery.

1. Material and methods

2.1. Compliance with ethical standards

The patients have given written informed consent for their participation in this research project prior to the inclusion of the study. Details which might disclose the identity of the patients were omitted. The authors follow the APA ethical standards.

The authorities in Greece does not prohibit the conducting of research protocols from scientists who treat patients in a private practice. There is no ethical commission which evaluates research projects from scientists in the private sector.

2.2. Study population

The outpatients with schizophrenia were recruited from [name] psychiatrist and cognitive behavioral psychotherapist and [name] clinical psychologist and cognitive behavioral psychotherapist from their own private practice. All participants were treated by both authors ambulant the last 15 years. All participants are treated monthly by [name] and participated in individual cognitive behavioral psychotherapy of 30 sessions in the past by [name].

A motivational interview was conducted with all the patients from [name] and [name] to enhance their motivation for participating in a group cognitive behavioral psychotherapy and rehabilitation. The patients have given written informed consent for their participation in this research project, and they were not paid for their participation. A total of 35 patients with schizophrenia participated in this study.

The inclusion and exclusion criteria of the study were the following: inclusion criteria: patients with schizophrenia between 19-60 years old, an IQ over 80 and patients must be treated in an ambulant psychiatric treatment. Exclusion criteria: Relapse and hospitalization, substance abuse and diagnosis of other psychotic disorders.

Finally, pharmacotherapy was not changed from [name] during the therapy, after the therapy and in the follow-up evaluation.

2.3. Study design

It is a non-randomized study. Patients were evaluated in a baseline assessment (T1)

and were allocated to the therapy group. Afterwards, they were evaluated in post therapy after 60 sessions (T2) and at a follow up of 6 months after the end of the therapy (T3).

2.4. Therapists

[name] and [name] were the therapists. [name] was the main therapist for the subprograms of IPT cognitive differentiation, social perception and verbal communication and [name] the co-therapist. [name] was the main therapist for the subprograms of IPT social skills and problem-solving and for the MCT for psychosis. [name] was co-therapist. Both therapists are well trained by IPT and MCT.

2.5. Intervention

IPT is a group therapy for patients with schizophrenia and contains 5 subprograms: Cognitive differentiation (neurocognition), social perception (social cognition), verbal communication, social skills and interpersonal problem-solving and presents an efficacious and evidence-based program for patients with schizophrenia (Roder et al., 2008, 2010). IPT was translated in Greek and was implemented with success from our research group ([name] et al., 2016, 2019, 2020, Roder et al., 2007. IPT was implemented also from other research groups in Greece with very good results (Poulou et al., 2024). In other words, IPT is well known and established in Greece.

All 5 subprograms of IPT in 50 biweekly sessions of 1 hour were implemented in this study.

MCT presents an efficacious and evidence-based group rehabilitation program for many mental health disorders. 10 biweekly sessions of one hour of MCT for psychosis were implemented in this study after IPT. It is the first implementation of MCT in Greece.

The implementation of this therapy was conducted in 8 small groups: 1 (5 patients), 2(2 patients), 3(8 patients), 4(8 patients), 5(3 patients), 6(3 patients), 7(3 patients), 8(3 patients).

2.6. Measures

2. 6. 1 WAIS

WAIS was implemented to all patients from [name] for the evaluation of IQ before

the baseline assessment of this research project (Aster. 2006).

2. 6. 2. Cognition (proximal outcome)

Neurocognition (speed of processing, working memory, visual memory, reasoning and problem-solving) of MCCB were used. Working memory was evaluated with the Letter Number Span using the Greek translation (Gold et al., 1997; Nuechterlein & Green, 2006, [name], 2007a). The Greek verbal memory test was used to evaluate verbal memory-oral and written (Kosmidou, 2010). Social cognition (MSCEIT-emotional intelligence) of MCCB (Nuechterlein & Green, 2006) and social perception scale using the Greek translation were also used (Garcia et al., 2003; [name] et al., 2007b; Ruiz et al., 2005). A blinded rater (Msc. Clinical psychology) has given the above tests before the therapy, after the therapy and in the follow-up of 6 months.

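### Cognitive tests are repeated at three visits in a single group with test forms unstated and no allowance for retest gain, so any practice gain is counted as therapy effect

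*Combined protocol and SAP*

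**What the plan says.** Section 2.6.2 (Cognition) lists the performance tests. For neurocognition: "Neurocognition (speed of processing, working memory, visual memory, reasoning and problem-solving) of MCCB were used". It adds: "Working memory was evaluated with the Letter Number Span using the Greek translation". It also names the Greek verbal memory test and, for social cognition, MSCEIT and the social perception scale. On timing it says: "A blinded rater (Msc. Clinical psychology) has given the above tests before the therapy, after the therapy and in the follow-up of 6 months". No form, version, order of forms or practice session is given for any test at any visit.

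Section 2.2 gives the sample: "A total of 35 patients with schizophrenia participated in this study". Section 2.3 says that patients were assessed at baseline "and were allocated to the therapy group", and no other group is described.

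Section 2.7 specifies a general linear model for repeated measures, a Bonferroni correction (number of comparisons not given), control of confounders (not named), regression and effect sizes. Practice or retest effects are not mentioned. The Abstract reports: "Significant effects were found in neurocognition, symptoms, functional outcomes and recovery".

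**The concern.** Scores on performance tests can rise on repetition because patients remember items or become familiar with the task. Such a rise has the same direction as benefit. In a single group, exposure to therapy and number of previous test sessions increase together from T1 to T2, so a test of change over visits cannot tell one from the other. A gain still present at T3 would look like a maintained effect.

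The two safeguards in the plan do not address this. Rater blinding limits biased scoring but does not stop a patient from remembering material. Bonferroni limits chance findings across several tests but leaves a systematic shift in each test in place.

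Neurocognition and social cognition are part of the main hypothesis in the Introduction, and the neurocognition result is reported as a finding. At stake is whether that finding can be read as an effect of IPT plus MCT.

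**Working it through.** The document gives no alpha, SD, effect size, retest correlation or sample-size calculation, so there is no stated figure to reproduce. One count can be checked: the eight groups in Section 2.5 sum to 5+2+8+8+3+3+3+3 = 35, which agrees with Section 2.2.

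**Inputs**
- From the document: n = 35, one group, tests at T1, T2 and T3.
- Assumed: retest gain d (in baseline SD), test-retest correlation r, equal SD at both visits, no true change, two-sided alpha of 0.05 or 0.05/3. The latter would apply if Bonferroni covered the three pairs of visits.

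**Method.** The T1-T2 contrast is treated as a paired t test, a simplification of the repeated-measures model.

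- Standardised paired difference: dz = d / sqrt(2(1 - r))
- Noncentrality: dz × sqrt(35), with 34 degrees of freedom

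For d = 0.2:
- r = 0.7: dz = 0.2 / sqrt(0.6) = 0.258; noncentrality 0.258 × 5.916 = 1.53
- r = 0.8: dz = 0.2 / sqrt(0.4) = 0.316; noncentrality 0.316 × 5.916 = 1.87

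**Chance that retest gain alone is declared significant**

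| Gain d | alpha | r = 0.6 | r = 0.7 | r = 0.8 |
|---|---|---|---|---|
| 0.1 SD | 0.05 | 10% | 12% | 15% |
| 0.2 SD | 0.05 | 25% | 32% | 44% |
| 0.3 SD | 0.05 | 49% | 61% | 78% |
| 0.2 SD | 0.05/3 | 13% | 18% | 27% |
| 0.3 SD | 0.05/3 | 31% | 42% | 62% |

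With no gain, the chance equals alpha (5% or 1.7%).

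**What reducing the gain would achieve.** At r = 0.7 and alpha 0.05, a gain of 0.4 SD gives 84%. Halving it to 0.2 SD gives 32%, still far above 5%.

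**Precision of an observed change.** The 95% half-width is 2.032 × sqrt(2(1 - r)) / sqrt(35):
- r = 0.7: 2.032 × 0.775 / 5.916 = 0.27 SD
- r = 0.8: 2.032 × 0.632 / 5.916 = 0.22 SD

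For the interval to lie wholly above an assumed benchmark of 0.3 SD, the observed change must exceed 0.30 + 0.22 = 0.52 SD (r = 0.8) to 0.30 + 0.27 = 0.57 SD (r = 0.7).

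**The case against.** The strongest reply is that much of this rests on silence. Naming an instrument does not fix its item set, and the document never says that identical items were reused. A reader might infer that no parallel forms were used and that the neurocognition endpoint therefore contains item learning. The text supports neither statement, only that the forms are not stated. This part of the reply stands.

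A reader might also infer that patients met these tests for the first time at T1, so that the largest practice step falls in the therapy interval. That is not supported either. Section 2.2 says that both therapists had treated the patients over the previous 15 years, and earlier exposure to the tests is not described in either direction. The length of T1-T2 is also unclear: 60 sessions take 60 / 2 = 30 weeks at two per week, but 60 × 2 = 120 weeks at one per fortnight. How much learning survives such a gap is unknown.

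It can also be said that this is largely a consequence of having no comparator. That is right. An equally retested control group would be expected to carry the same gain, and it would cancel in the comparison. Alternate forms reduce memory for items but not familiarity with testing, so they would not replace a control. The point remains useful because it concerns performance tests in particular and part of it can be handled in reporting.

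Finally, the Abstract does not list social cognition among the significant effects for the full sample, although those tests were repeated too. This is weak evidence against a uniform practice effect. It does not exclude one in the neurocognitive tests, and the Abstract does list social cognition for the treatment-resistant subgroup.

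**Conclusion.** The concern holds in a limited form. The plan repeats performance tests at three visits in one group, leaves the forms unstated, and analyses change without allowing for retest gain. Whatever practice gain occurred is counted as therapy effect.

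The size is conditional. With 35 patients, r of 0.7 to 0.8 and no true change, a gain of 0.2 to 0.3 SD would be declared significant in 32% to 78% of trials at 0.05, and in 18% to 62% at 0.05/3. The gains, correlations and Bonferroni divisor are assumptions. The figures show what a modest gain could do, not what happened here.

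It would be tempting to conclude that the reported neurocognition effect is a practice artefact. The document does not support that: it gives no scores, and a true improvement is equally compatible with it. The supported conclusion is that the design and analysis cannot separate the two.

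**What to change.** The Abstract already reports results, so the change belongs in analysis and reporting:

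1. State the form or version of each cognitive test used at T1, T2 and T3.
2. For every test in Section 2.6.2, including MSCEIT and the social perception scale, report T1-T2 and T1-T3 change with its confidence interval beside a published retest gain for that test, where one exists. Give the population and retest interval of that source.
3. Do not attribute change to therapy where the interval includes that gain.
4. Reword the neurocognition conclusion in the Abstract as uncontrolled pre-post change that may include practice effects. The subgroup sentence on neurocognition and social cognition needs the same caution.
5. For any further cohort, use alternate forms where they exist.

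The work is small: one table column and a few sentences. There are two real downsides. A published gain may come from another population or interval, so it guides interpretation and is neither a correction nor a strict pass mark. Fewer effects will also be claimed, given the 0.52 to 0.57 SD needed against a 0.3 SD benchmark. A change above the benchmark would still be uncontrolled.

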2.6.3. Psychopathology (proximal outcome)

Psychopathology was evaluated from PRYRAT (Haddock et al., 1999) and PANSS (Lykouras et al., 2005). A blinded rater (M. D.) has conducted the PSYRAT and PANSS before the therapy, after the therapy and in the follow-up after 6 months.

2.6.4. Functional outcome (proximal outcome)

Functional outcome was from WHODAS evaluated (Koumpouros et al., 2018; WHO, 2001). A blinded rater (Msc. Clinical psychology) has given the above tests before the therapy, after the therapy and in the follow-up of 6 months.

2.6.5. Recovery (proximal outcome)

Recovery was evaluated from the Greek version of RAS-DS (Hancock et al., 2019, 2023). RAS-DS is a reliable and valid scale (Hancock et al., 2015, 2019; Honey et al., 2023; Ramesh et al., 2024). A blinded rater (Msc. Clinical psychology) has given the above tests before the therapy, after the therapy and in the follow-up of 6 months.

2. 7. Statistical analysis

SPSS version 13 has been used for statistical analysis. A general linear model for repeated measures was chosen. A general linear model understands and quantifies the relationship between therapy and the proximal outcomes. A Bonferroni correction was made. Confounding variables were controlled. A regression analysis was conducted. A

regression analysis quantifies the strength between the variables (therapy and proximal outcomes) Effect sizes were also calculated. A statistical analysis (general linear model, effect sizes, regression analysis) was conducted for the 35 participants and afterward a second analysis was conducted (general linear model, effect sizes, regression analysis) focusing on the group of treatment resistant schizophrenia (Bortz & Döring, 2002; Cohen, 1988).

References

Bortz, J., & Döring, N. (2002). *Forschungsmethoden und Evaluation für Human- und Sozialwissenschaftler*. Berlin: Springer.

Cohen, J. (1988). *Statistical Power Analyses for Behavioural Sciences*. Erlbaum, Hillsdale, NJ.

Sydney.

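### All 35 patients were treated and no comparator is described, so the analysis estimates change over T1–T3 and cannot support the therapy-effect wording of section 2.7 or the abstract's effectiveness conclusion

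*Combined protocol and SAP*

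**What the plan says.** Section 2.3 calls the study non-randomized. Patients had a baseline assessment (T1), "and were allocated to the therapy group", and were assessed again after 60 sessions (T2) and six months after therapy ended (T3).

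Section 2.2 gives the sample: "A total of 35 patients with schizophrenia participated in this study". Section 2.5 gives the delivery: "The implementation of this therapy was conducted in 8 small groups", with the size of each group listed.

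Section 2.7 chooses a general linear model for repeated measures and interprets it: "A general linear model understands and quantifies the relationship between therapy and the proximal outcomes". It adds a regression: "regression analysis quantifies the strength between the variables (therapy and proximal outcomes". It also states "Confounding variables were controlled", without naming a variable or a method. The same analyses are repeated in the treatment-resistant patients.

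The main hypothesis in the Introduction is that the combination is both effective and efficacious. The abstract reports significant effects and concludes in favour of effectiveness, with significant effects also reported for the treatment-resistant subgroup.

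**The concern.** A statement about the effect of therapy needs some information on what would have happened without it. That could come from untreated patients, an untreated period in the same patients, or an external comparator. The documents describe none of these. The treatment-resistant patients are a subset of the treated sample, so they are not a comparator either.

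What is at stake is the headline conclusion. A significant time effect is what a working therapy would produce. It is also what the following could produce with no therapy effect at all:

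- practice on a test battery given three times;
- natural course;
- regression to the mean;
- patient expectancy;
- non-specific attention from the group or the therapists.

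The analysis cannot tell these apart, yet sections 2.7 and the abstract are worded as if it could.

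**Working it through.** **1. Who was treated.** Group sizes from section 2.5: 5 + 2 + 8 + 8 + 3 + 3 + 3 + 3 = 35. This reproduces the total of 35 in section 2.2, so no participant is left as a comparator.

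**2. What the model can estimate.** There are 35 patients × 3 visits = 105 rows. If therapy is coded before/after, its column is 0 at T1 and 1 at T2 and T3, so

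after-therapy = T2 + T3,

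which is an exact sum of two columns already in the model.

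| Columns | Number | Rank |
|---|---|---|
| Intercept, T2, T3, after-therapy | 4 | 3 |
| The same + 3 patient-level covariates | 7 | 6 |
| The same + each covariate × T2 and × T3 | 13 | 12 |

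The three covariates are an illustration, because section 2.7 names none. The missing rank is the same each time: therapy against time. Coding therapy instead as an indicator equal to 1 for every patient, with therapy × T2 and therapy × T3, gives 6 columns and rank 3. Only the intercept and the two visit contrasts (T2 − T1 and T3 − T1) can be estimated.

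**3. Limit of step 2.** The result depends on the coding. If the predictor were a quantity that differs between patients, such as a hypothetical number of sessions attended multiplied by after-therapy, the 4-column matrix would have rank 4. The documents describe no such variable. Its coefficient would compare patients who differ for reasons nobody assigned, so it would be an observational association.

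**4. Illustration for the cognitive tests only.** Suppose the therapy effect is zero and there is a retest gain of d = 0.2 SD. The gain, the correlation r between visits, the two-sided test level and the Bonferroni divisor are all assumptions; the documents give none of them. For the paired T1–T2 test with n = 35 (34 df):

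d_z = d / √(2(1 − r)), noncentrality = d_z × √35.

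- r = 0.5: d_z = 0.2 / √1.0 = 0.200, noncentrality 1.18, probability of significance at 0.05 = 21.0%.
- r = 0.8: d_z = 0.2 / √0.4 = 0.316, noncentrality 1.87, probability of significance at 0.05 = 44.4%.

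At an assumed 0.05/12 the two figures are 4.0% and 13.5%. The three-visit time test (compound symmetry, gain kept at T3, F with 2 and 68 df) gives 20.5% to 45.7% at 0.05 and 3.9% to 14.9% at 0.05/12. No rate is offered for symptoms, function or recovery, or for the treatment-resistant subgroup, whose size is not stated.

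**The case against.** **A single-group study is legitimate, and the model is valid for it.** This stands. The general linear model is a sound way to describe within-patient change. The objection is to the inference drawn from it, and nothing here says that a control arm had to be added.

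**The design is visible.** Non-randomized appears in the official title and in section 2.3, and one therapy group is plainly described. A careful reader can work it out. But a non-randomized study may have a control group, the documents never state that this one has none, and disclosure would not license the effectiveness conclusion.

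**The word relationship need not be causal.** True of section 2.7 read alone. Beside a hypothesis of efficacy and a conclusion of effectiveness, it will be read as a treatment effect.

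**There are safeguards.** Section 2.2 says "pharmacotherapy was not changed", which weakens drug change as a rival explanation. Two other apparent safeguards cannot be counted. Raters are called blinded in sections 2.6.2 to 2.6.5, but with one group there is no allocation to be blind to, and blinding to visit is not stated. Relapse and hospitalization are exclusions, but the timing is not stated. Applied at entry, they suggest stable patients; applied during the study, they would remove patients who worsened. Section 2.2 also says "All participants were treated by both authors ambulant the last 15 years", which may suggest a settled course, but it means the therapists were the patients' long-standing clinicians, so attention and expectancy remain open. The text does not support ranking the rival explanations.

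**Confounding was controlled.** No covariate is named, and step 2 shows that a patient-level covariate cannot supply the missing untreated course.

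**Conclusion.** The point holds and must be fixed, because it concerns the headline conclusion in both analysed populations. The design supports a statement about change over T1, T2 and T3 in one treated cohort of 35, and the same kind of statement for the treatment-resistant subgroup. It does not support attributing that change to the therapy. This rests on the count of treated patients and on the absence of any described comparator or untreated period, and needs no numerical assumption.

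Three stronger readings might be inferred, and the documents support none of them:

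- *The therapy does not work, or the reported changes are spurious.* The design cannot show this either; it is silent on the cause of the change.
- *Therapy could never be separated from time under any analysis.* The rank result is for therapy coded before/after or as constant across patients. The regression predictor is not defined, and one that varies between patients would be estimable, though only as an observational association.
- *The 21% to 44% range is this trial's false-positive rate.* It is an illustration under an assumed gain, correlation and test level, for cognitive tests only. At the stricter assumed level it falls to between 4.0% and 13.5%. The conclusion is unchanged if these figures are set aside.

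**What to change.** (a) **Abstract.** Limit the conclusion, for the whole sample and for the treatment-resistant subgroup, to change over T1–T3 in one uncontrolled treated cohort that cannot be attributed to the therapy.

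(b) **Main hypothesis.** Leave it as it stands, since results are already reported and rewriting it now would fit it to them. Add a statement that this design cannot test efficacy or effectiveness against a comparator.

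(c) **Section 2.7.** Describe the general linear model as estimating within-patient change. Report the T1–T2 and T1–T3 mean changes with confidence intervals. State the regression predictor and its coding, and claim no more than that coding allows. In place of the unqualified "Confounding variables were controlled", list the covariates actually entered and state that they do not address retest practice, natural course, regression to the mean, patient expectancy or non-specific group or therapist attention.

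(d) **Section 2.3.** Add *single group, no comparison arm* beside the description as non-randomized.

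The cost is rewording, plus mean changes and intervals from data already collected. The downside is a less favourable conclusion.

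### Section 2.7 says the regression and the general linear model quantify how therapy relates to outcome, but with a single therapy group neither can give a therapy effect distinct from change over time

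*Combined protocol and SAP*

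**What the plan says.** Section 2.7 names two models and gives both the same purpose. On the GLM for repeated measures: "A general linear model understands and quantifies the relationship between therapy and the proximal outcomes". On the regression: a "regression analysis quantifies the strength between the variables (therapy and proximal outcomes". It adds "Confounding variables were controlled", without naming the variables or the model they entered. Both models are applied to the 35 participants and then to the TRS subgroup, whose size is not given.

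The design is set out earlier:

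- Section 2.2: "A total of 35 patients with schizophrenia participated in this study".
- Section 2.3: a non-randomized study in which patients were assessed at baseline (T1), placed in the therapy group, and assessed again after the 60 sessions (T2) and six months later (T3). No second group is described.
- Section 2.5, programme: "All 5 subprograms of IPT in 50 biweekly sessions of 1 hour were implemented in this study", and "10 biweekly sessions of one hour of MCT for psychosis were implemented in this study after IPT".
- Section 2.5, delivery: the therapy "was conducted in 8 small groups: 1 (5 patients), 2(2 patients), 3(8 patients), 4(8 patients), 5(3 patients), 6(3 patients), 7(3 patients), 8(3 patients".

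The abstract says that both models were used, reports significant effects, and concludes that the study supports the effectiveness of the combination.

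**The concern.** To measure how strongly therapy relates to an outcome, therapy must vary in a way that can be told apart from everything else that varies. Here every patient received the programme, and the only contrast is between earlier and later visits of the same people. Section 2.7 nevertheless describes both models as measuring the relation of therapy to outcome.

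Two things are at stake. First, a within-patient change may be read as an effect of therapy, and the abstract's conclusion invites that reading. Second, with two models listed side by side in two analysis sets, a reader may count the regression as support beyond the GLM when it may be the same contrast computed another way.

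**Working it through.** **1. Inputs.** The group sizes in section 2.5 sum to 5 + 2 + 8 + 8 + 3 + 3 + 3 + 3 = 35, which reproduces the total in section 2.2. Sessions: 50 + 10 = 60, the same planned amount for everyone. The eight groups are units of delivery of one programme, so they do not make therapy vary.

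**2. Therapy as a patient-level variable.** Take y_i = b0 + b1·x_i + e_i with x_i = 1 for all 35.

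- The variance of x is 0.
- X'X = [[35, 35], [35, 35]], with determinant 35·35 − 35·35 = 0.
- The rank is 1 for 2 columns. Only the sum b0 + b1 can be estimated, so b1 has no estimate.

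Covariates do not help: the therapy column still equals the intercept column, so the rank stays at least one short. The same holds in any subset. For a TRS subgroup of m patients the determinant is m·m − m·m = 0.

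**3. Therapy as before/after, with patients linked.** Take y_it = a_i + b·z_t + e_it, with z = 0 at T1 and 1 afterwards.

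- Columns: 35 patient terms + 1 = 36. The rank is 36, so b can be estimated.
- With T1 and T2 only, b is the mean over patients of (y_i2 − y_i1). With T1 and T3 only, it is the mean of (y_i3 − y_i1).
- With all three visits, b is the mean of [(y_i2 + y_i3)/2 − y_i1], the average of those two changes.

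Each of these is a contrast already contained in the time effect of the repeated-measures GLM. The estimates and tests agree when both models use the same visits, error structure and covariates. Section 2.7 does not establish that they do.

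**4. Can b be separated from time?** Add a three-level time factor with indicators d2 (T2) and d3 (T3).

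- At every visit z = d2 + d3.
- Columns: 35 + 1 + 2 = 38. The rank is 37, so therapy is exactly aliased with time.
- If time is entered as a straight line instead, the rank is 37 of 37, but b is then identified only by assuming that change without therapy would be linear. The documents state no such assumption.

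In words: expected change from T1 to T2 = therapy effect + practice on repeated tests + regression to the mean + secular change. The data supply one quantity for several unknowns. Patient characteristics fixed at baseline do not separate them, because they do not distinguish the visits of one patient.

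**5. What the documents leave open.** The regression's outcome, predictor, coding of therapy and covariates are not stated. Step 2, step 3 and a model with baseline predictors are all possible. None of them measures the strength of therapy as distinct from time.

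**The case against.** The strongest reply is that the two sentences in section 2.7 describe methods in general terms and do not specify a model. Since all outcomes are scheduled before and after therapy and a repeated-measures model is named, the natural meaning of therapy is the before/after factor, and that coefficient can be computed. Section 2.2 adds that medication was not changed, which removes one rival explanation. On this view the point is only about wording.

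Much of this stands. A reader might infer that no therapy coefficient of any kind can be estimated; step 3 shows that this is too strong. What fails is the separation of therapy from time. Unchanged medication does not rule out practice effects, regression to the mean or other change over time.

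A reader might also infer that the abstract rests on the regression as independent proof. It does not say so: it states that both models were used and reports no separate regression result. Nor do the documents show that the regression was wrong or merely exploratory, because the model fitted is not disclosed. If baseline variables were the predictors, it may be a sound analysis of who improves, though not the one section 2.7 describes.

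The reply that this is only wording does not stand. Those sentences are the only account of what the models estimate, and they attribute to the design a property it lacks.

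**Conclusion.** The point holds in this form: section 2.7 attributes to both models, in both analysis sets, a measure of therapy that a one-group design cannot supply separately from time. With 35 of 35 patients treated, a patient-level indicator has no estimate. A before/after indicator repeats the GLM's change from baseline when the models match, and is not additional evidence.

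This rests on the design as described: one therapy group, one programme, and no comparator, attendance or dose variable. It needs no assumed effect size, correlation or TRS sample size. The GLM contrast remains usable as within-patient change over time. No reported figure is shown to be wrong; what changes is what the results may be said to show.

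**What to change.** - In section 2.7, replace both statements about therapy, for the 35 and for the TRS set, with: *The models estimate within-patient change from T1 to T2 and from T1 to T3; without a control group this is change over time, not an effect of therapy.*
- Report the mean changes with confidence intervals, and state whether the intervals are adjusted under the Bonferroni correction that section 2.7 mentions.
- Disclose the outcome, predictor and covariates of the regression that was run, and say which model the control of confounding refers to. If therapy was coded as before/after, do not present the regression as evidence separate from the GLM. If baseline variables were the predictors, describe it as prediction of outcome, not strength of therapy.
- Limit the abstract's effectiveness conclusion to within-patient change.

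Cost: text changes in section 2.7 and the abstract, disclosure of a model already fitted, and intervals computed from T1, T2 and T3 scores already scheduled for collection. No new data are needed. The price is one fewer analysis offered in support of effectiveness and a narrower conclusion.
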